**Inclusion Criteria:**

- BMI at least 18 but less than 25 kg/m^2

**IRB #:** 15-1052  
**Project Title:** Reprometabolic Syndrome Mediates Subfertility in Obesity  
**Principal Investigator:** [name]

- No history of chronic disease affecting hormone production, metabolism or clearance
- No use of medications known to alter or interact with reproductive hormones or insulin metabolism (e.g. thiazolidinediones, metformin)
- No use of reproductive hormones within 3 months of enrollment
- Normal prolactin and thyroid stimulating hormone levels at screening
- History of regular menstrual cycles every 25-35 days
- Use of a reliable method of contraception (female or male partner sterilization; IUD; abstinence; diaphragm)
- Normal hemoglobin A1c
- Screening hemoglobin  $\geq 11\text{gm/dl}$

Exclusion criteria:

- Women with a baseline dietary assessment indicative of  $>40\%$  daily calorie consumption from fat (as calculated based upon initial 3 day diet record) will be excluded, as the impact of increasing their dietary fat intake may be minimal.
- Women with current or a history of diabetes, prediabetes, or gestational diabetes.
- Women with fasting triglycerides  $>300\text{mg/dl}$  at screening will be excluded, as they might be at risk for acute elevation of triglycerides and even pancreatitis if placed on a high fat diet.
- Inability to comply with the protocol. Individuals who travel frequently, or who eat most of their meals outside of their home will be excluded, as it will be difficult to impossible for them to comply with the diet, to pick up the food cartons, etc.
- Because high proportions of dairy fat will be needed to attain 48% calories from fat in the diet, vegans and lactose intolerant individuals will be excluded.
- Pregnant women or women planning to become pregnant will be excluded.

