Aim 1B will induce a chronic model of the reprometabolic syndrome by administering a eucaloric high fat diet for one month while monitoring gonadotropin pulsatility and daily urinary reproductive hormone excretion. In Aim 1b we want to demonstrate that a eucaloric high fat diet can induce insulin resistance and/or elements of the reprometabolic syndrome in women.

Aims 2 and 3 will be an exemption of analysis from the procedures performed and samples collected in Aims 1.A and 1.B. They will not require additional enrollment of study subjects or additional procedures.

**Pilot:** consisted of the Principle Investigator testing out the proposed diet intervention for Aim 1.B. The test diet was given for two weeks. There were no subjects consented or enrolled, and the Investigator declined compensation.

**Aim 1A:** will consist of four visits: a screening visit (12 hour fast required) and three study visits. During the screening visit participants will be provided with instructions and supplies to collect their daily morning urine and to use home ovulation predictor kits. Determining the day of ovulation will allow us to better predict the timing of the following menses (which almost always occurs 12-15 days after the urinary LH surge identified by the ovulation predictor kit). Accurate prediction of cycle Day 1 will permit more efficient scheduling of the frequent sampling studies, which must occur within a window of 1-4 days after the onset of menses (cycle days 2-5). We will ask participants to track their menstrual cycle by recording the day they start their period and the day that they ovulate and notify the study coordinator when evidence of a urinary LH surge has occurred. This will involve dipping a test stick in urine for several days to see if it changes color. Additional ovulation prediction kits will be provided if needed to the participants at the Visit 1 & 2. Participants will be administered saline only (limited subsample), saline + heparin infusion, and an insulin/intralipid/heparin infusion over 6 hours. Each participant will receive at least a saline+heparin infusion and an insulin/intralipid/heparin infusion, but

IRB #:

15-1052

Project Title:

Reprometabolic Syndrome Mediates Subfertility in Obesity

Principal Investigator: [name]

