the order in which the treatments are given will be randomly assigned. The insulin/intralipid/heparin infusion will consist of 20% lipid emulsion (45ml/h), heparin (24 units/kg/hr), and insulin (20 mU/m2/min) under euglycemic clamp conditions (maintained by using dextrose). Saline will be infused at a rate of 200 ml/h with heparin (24 units/kg/hr). During the saline only visit, heparin will not be infused. We have added a 'saline only' visit to validate the findings of the saline+heparin infusion study and to rule out any independent effect of heparin. At the same time, participants will undergo a 6-hour frequent blood sampling session at each visit. Muscle oxygenation will also be measured before and at 4 hours of both infusions. Partial thromboplastin time (PTT) levels will be followed with heparin infusion adjustments as needed to avoid over-anticoagulation. Each visit will be performed in the early follicular phase of the menstrual cycle and will be completed in consecutive cycles whenever possible, but no longer than within 4 cycles from the first study. Please see table description below:

	Pre-cycle 1	Visit 1	Visit 2	Visit 3
Visit#	L0=screen	L1	L2	L3
Description/Duration	2 hours	6 hours Concurrent FSS infusion*	6 hours Concurrent FSS infusion*	6 hours Concurrent FSS infusion*
Cycle Day		2-5	2-5	2-5
History	X			
Physical	X			
Pregnancy Test		X	X	X
Routine safety labs (CBC/CMP)	X	X	X	X
Hemoglobin A1C	X			
Prolactin	X			
Fasting Lipid Panel	X	X	X	X
TSH	X			
PTT	X	X	X	X
FFA	X	X	X	X
Informed Consent	X			
Weight	X	X	X	X
Ovulation Prediction Kits	X	X	X	
Frequent blood sampling		X	X	X
Administration of GnRH		X	X	X
Muscle Oxygen Measurement		X	X	X
Infusion*		X*	X*	X*

\*participants will receive either an insulin +lipid + heparin infusion, a heparin + saline (control), or saline only in random order

IRB #: 15-1052  
Project Title: Reprometabolic Syndrome Mediates Subfertility in Obesity  
Principal Investigator: [name]

**Aim 1B:** will consist of 11 in-person visits.

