### ***Risks of medications to be administered:***

***Insulin:*** recombinant human insulin (Humulin) will be administered. Its chief side effect is hypoglycemia. As all participants will be undergoing glucose monitoring every 5 minutes during the clamp studies, their glucose level will be continuously adjusted by adjusting the intravenous dextrose to maintain blood glucose within a 90-100 mg/dl range.

***Intralipid (Aim 1A only):*** Intralipid will be administered as an intravenous infusion. Side effects reported for this compound include headache, dizziness, nausea, vomiting, sweating, difficult or labored breathing, or, rarely, anaphylactic type reactions have been reported. Participants will be monitored throughout the infusion in the CTRC, where epinephrine is readily available for any allergic reaction.

***Dextrose (20%):*** will be administered to maintain the blood glucose level between 90-110 mg/dl.

***Heparin:*** will be used in concert with the intralipid infusion to maintain catheter patency and stimulate lipolysis. Adverse reactions to high doses of heparin include hemorrhage and thrombocytopenia. Very long term use (months) has been associated with osteopenia. Heparin will be used at very low doses in this experiment and may induce short term anticoagulation but would not be expected to cause thrombocytopenia or osteopenia at this low dose.

IRB #:

15-1052

Project Title:

Reprometabolic Syndrome Mediates Subfertility in Obesity

Principal Investigator: [name]

Anaphylactic reactions have been reported to occur with heparin, and participants will all be given heparin at the CTRC where nursing personnel monitor them continuously and epinephrine is readily available. In addition:

- 1) aPTT will be confirmed before participants leave the CTRC to ensure levels are not in excess of the targeted degree of therapeutic anticoagulation in the outpatient setting (aPTT < 120 seconds -- the upper target of therapeutic anticoagulation used in inpatient or outpatient setting).

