- 2) aPTT will be measured during peak infusion (mid-interval) at ~3 hours. The heparin infusion rate will be reduced by 50% if aPTT is > 100, and by 25% (to standard anticoagulation dosing) if the aPTT is 80-100. Levels will be re-measured at 6 hours (toward the end of the infusion) to ensure the aPTT is < 120 secs before allowing the participant to be discharged. If the 6 hour aPTT is > 120, another will be checked at 7 hours, one hour after discontinuation of the heparin (t=7 hours) to ensure that the aPTT is < 120 prior to discharge or on a downward trajectory that ensures aPTT<120 by time of discharge.
- 3) Patients will be counseled about possible side effects of longer clotting times, behaviors to avoid in the coming hours, what to look for and what steps to take should symptoms develop. Aspirin and Ibuprofen should be avoided for at least 2 hours if the patient is discharged with an abnormal aPTT (>35 seconds).

**GnRH (gonadotropin releasing hormone):** GnRH is a 10 amino acid peptide that has a short serum half-life and minimal known antigenicity. If given in large doses, it has been associated with a risk of multiple pregnancy. Our participants will all be using contraception and tested for pregnancy at the onset of each assessment.

*Iron Supplements:* Common side effects include an upset stomach, pain, constipation or diarrhea, nausea, or vomiting.

**Risks to pregnant women:** Although none of the medications listed above are contraindicated in pregnant women, there is no reason for a pregnant woman to be exposed to any of the potential risks above. Our goal is to study how obesity and a high fat diet might mediate abnormal reproduction in women, and pregnant women are not eligible for these studies. To avoid any possible exposure, participants will be included only if they are using a reliable non-hormonal method of contraception and they or their partner has been sterilized. They will only undergo frequent sampling studies in the early follicular phase of the menstrual cycle, and thus are extremely unlikely to be pregnant with a normal gestation if they have just had a menstrual period. As a further safeguard, we will verify the menstrual history with the participant before each frequent sampling study and perform a high-sensitivity urine pregnancy test (40 mIU/ml of hCG) prior to beginning any of the blood sampling sessions.

**IRB #:** 15-1052  
**Project Title:** Reprometabolic Syndrome Mediates Subfertility in Obesity  

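### Aim 1A eligibility has no criterion for the heparin and lipid hazards that the protocol names, and the screening PTT has no stated entry use

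*Combined protocol and SAP*

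**What the plan says.** **Exposure.** The Aim 1A text under Study Design and Research Methods states: "Each participant will receive at least a saline+heparin infusion and an insulin/intralipid/heparin infusion". The order is random and each infusion lasts 6 hours. The active "infusion will consist of 20% lipid emulsion (45ml/h), heparin (24 units/kg/hr), and insulin (20 mU/m2/min) under euglycemic clamp conditions". The control is saline with heparin at the same hourly rate. A limited subsample has a third visit with saline alone: "During the saline only visit, heparin will not be infused".

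**Named hazards.** Under Risks of medications to be administered, the protocol says "Anaphylactic reactions have been reported to occur with heparin" and "Adverse reactions to high doses of heparin include hemorrhage and thrombocytopenia". It adds that the study's heparin doses are very low, may anticoagulate for a short time, and are not expected to lower platelets. For the lipid emulsion it reports rare anaphylactic-type reactions.

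**Eligibility.** One list serves both parts of Aim 1. Its drug item reads "No use of medications known to alter or interact with reproductive hormones or insulin metabolism". Its disease item is confined to chronic conditions acting on hormones. The remaining items concern BMI, recent hormone use, prolactin and TSH, cycle regularity, contraception, HbA1c, hemoglobin, dietary fat, diabetes, triglycerides, compliance, vegan diet or lactose intolerance, and pregnancy.

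**Screening.** The Aim 1A visit table marks history, physical, CBC/CMP and PTT at the screening visit. The Consent/Screening Process section describes the laboratory tests at intake as qualifying ones.

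**The concern.** Some women are more likely than others to be harmed by heparin or a lipid emulsion: those with a past reaction to either product, a bleeding or platelet disorder, or a drug that affects coagulation. Such features can be known before the first infusion. The protocol names the resulting harms but has no entry criterion for any of these features, and it draws PTT and a blood count at screening without saying what a PTT or platelet result would mean for entry. The participants are volunteers in a mechanistic study. What is at stake is their protection, and whether screening is applied the same way to each of them.

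The natural reassurance is that so little heparin is given that bleeding criteria are unnecessary. That depends on the description of the dose as very low, which the heparin monitoring rules in the same section contradict.

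**Working it through.** The documents give no figure to reproduce here. The check sets sections side by side and adds simple arithmetic.

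**1. Exposure.** Inputs: 12 women to complete Aim 1A; two infusion types with heparin, one of which also contains lipid; the saline-only visit has no heparin.
- Heparin infusions: 12 × 2 = 24.
- Lipid infusions: 12 × 1 = 12.

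**2. Hazards against entry criteria.**

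| Hazard named | Entry criterion | Information at screening | Safeguard once infusion begins |
|---|---|---|---|
| Anaphylactic reaction, heparin | None | History, physical | Continuous nursing, epinephrine |
| Anaphylactic-type reaction, lipid | None | History, physical | Monitoring throughout, epinephrine |
| Hemorrhage, heparin at high doses | None | History, physical, PTT, CBC | aPTT at about 3 and 6 hours, rate reductions, discharge check, counseling |
| Thrombocytopenia, heparin at high doses | None | CBC (assumed to include platelets) | CBC at each visit, no stated action |

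The nearest existing criteria are hemoglobin of at least 11 g/dl, which the protocol ties to blood loss from sampling, and triglycerides above 300 mg/dl, which it ties to the high-fat diet. Neither addresses the hazards in the table. They do show that the protocol turns screening results into entry limits when it intends to.

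**3. When each aPTT figure applies.**
- 80–100 and above 100 seconds: at about 3 hours into the infusion, for rate reductions of 25% and 50%.
- 120 seconds: at about 6 hours, and at 7 hours if needed, before discharge.
- 35 seconds: advice for the hours after discharge.

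None applies at screening.

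**4. The dose statements.** The starting rate is 24 units/kg/hr. The heparin rules say that a 25% reduction brings the rate to standard anticoagulation dosing. Taking the 25% off the starting rate:
- 24 × (1 − 0.25) = 18 units/kg/hr, the level the protocol calls standard.
- 24 / 18 = 1.33, so the starting rate is a third above that level.
- Without adjustment, 24 × 6 = 144 units/kg per visit, or 288 units/kg over two visits.

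The same rules provide for aPTT above 100 seconds in mid-infusion and above 120 seconds at 6 hours. This cannot be squared with doses described as very low.

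**5. Possible size.** The documents give no prevalence for the relevant histories. Assume p between 1% and 5%.
- Expected number among 12: 12 × 0.01 = 0.12 to 12 × 0.05 = 0.60 women.
- Chance of at least one: 1 − 0.99^12 = 0.11 to 1 − 0.95^12 = 0.46.

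This range is illustrative only; the gap in the text does not depend on it.

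**The case against.** The strongest reply is that risk control is not absent. A history and physical are taken, the intake tests are called qualifying, and a sensible investigator would probably turn away a woman with a known heparin reaction. During infusion there is continuous nursing, epinephrine at hand, aPTT checks with rate reductions, and a check before discharge. The safety officers review the protocol and the termination guidelines before enrollment. The protocol also ties hemorrhage and thrombocytopenia to high doses, and it handles other hazards, such as hypoglycemia and infiltration, without an entry criterion.

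Much of this stands. The documents do not require an exclusion for every hazard, and the gap concerns participant selection only. But the on-infusion safeguards act after exposure has begun, the anaphylaxis warning for heparin carries no dose qualifier, and the dose reassurance is contradicted by the protocol's own figures. Calling a test qualifying without a limit leaves the decision unwritten. Consent pages were not available, but entry criteria belong in the protocol.

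A reader might infer four stronger things that the documents do not support:
- **That susceptible women would be enrolled.** The text shows only that they meet every written criterion; clinical judgment at screening may stop them.
- **That a raised screening aPTT would force a heparin reduction and so alter that woman's lipolytic stimulus.** The rule acts on the value at about 3 hours, from 80 seconds upward. Nothing links a screening value to reaching that level, and the rule can apply to any woman.
- **That 35 seconds is a screening limit.** The protocol uses it only for advice after discharge.
- **That aspirin and ibuprofen must be barred before infusion.** The protocol addresses them only after discharge. Whether to go further is a clinical decision.

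**Conclusion.** The point holds as a gap in participant selection together with an internal contradiction on heparin dose. All 12 Aim 1A women are planned to receive heparin twice and lipid once, and none of the written criteria covers hypersensitivity to these products, bleeding or platelet disorders, or drugs affecting coagulation. PTT and CBC are drawn at screening, yet only hemoglobin carries an entry limit. Separately, the starting heparin rate is 1.33 times the level the protocol labels standard, while the risk text calls the doses very low.

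The number of women affected is probably below one under the assumed prevalence, but the named harms are serious and the correction is small, so it should be made. The point concerns participant safety and clear screening rules; it shows no bias in the LH pulse amplitude comparison. It assumes that the CBC includes a platelet count, that the 25% reduction is taken from the starting rate, and that no further criteria exist outside the protocol text.

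**What to change.** - Reconcile the eligibility list, as it applies to Aim 1A, with the heparin and lipid risk text, so that the hazards named there are addressed at entry. The investigator and safety officers should decide the criteria.
- State the eligibility use of the screening PTT and platelet count, with any limits set by the same people.
- Reconcile the statement that heparin doses are very low with the statement that a 25% reduction reaches standard anticoagulation dosing, and revise the risk description to match. This review takes no position on which statement or rate is right.

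The cost is a few lines in an amendment and an occasional volunteer screened out. No new test is needed, because the PTT, CBC, history and physical are already part of Aim 1A screening.

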### ***Potential Scientific Problems***

#### **Aim 1:**

Health-conscious women may not want to do a study that will involve high fat feeding, which is viewed as unhealthful. On the other hand, high fat food is generally quite tasty, the diet will be eucaloric and short term, which is exceedingly unlikely to have any harmful, long-term effects, and all food will be provided to participants for an entire month. Others have used diets as high as 45% fat in pregnant women with gestational diabetes with good outcomes, further evidence that a short term exposure to a diet high in fat will not cause long term adverse health consequences. We have chosen to utilize rigorous methods to check for compliance. Variability at baseline in fat consumption will also be controlled by excluding women who are already consuming a HFD (defined as  $\geq 40\%$  energy from fat). It is most important that we avoid any weight loss in the NWW consuming a high fat diet, as this would have the potential to confound our results. Weight loss has been associated with increased urinary gonadotropin excretion and decreased serum gonadotropins. Thus, while we maintain a eucaloric diet in Aim 1b, we will also weigh all of the participants weekly; assuring that they are consuming all of the food provided and measure fatty acid concentrations as a compliance marker.

Studies in lean men indicate unequivocal induction of increased hepatic insulin resistance after only 5 days of a eucaloric diet containing 65% calories from fat, and non-statistically significant increases in both glucose and insulin have been observed after a 5-day high fat eucaloric diet in 12 women and men. It is possible that women will be more resistant to a HFD intervention that is only 48% energy from fat. However, Bergougnian, et al, have demonstrated clear-cut increases in FFAs after 72 hours on a eucaloric HFD diet identical to the one we plan to administer. While we expect that the much longer exposure we propose (than what has been done in prior work) will likely be needed to achieve measurable changes in insulin sensitivity. We will not leave this to chance and have taken precautions described in the beginning of this aim to assure that we create a high fidelity

**IRB #:** 15-1052  
**Project Title:** Reprometabolic Syndrome Mediates Subfertility in Obesity  
**Principal Investigator:** [name]

model of hyperinsulinemia and elevated FFAs, which may require initial adjustment of our intervention (to include more simple carbohydrate or a brief period of hypercaloric consumption) before proceeding with the full experiment.

**Aim 2:**

We anticipate that a one-month exposure to an HFD will decrease insulin sensitivity, but outlined above in Aim 1, we will perform preliminary investigations to assure that the intervention is sufficient to cause detectable changes in gonadotropins. We will adjust our experimental design before we begin if it should be necessary.

**Aim 3:**

Because this aim is relatively exploratory, it would be ideal to include as many analytes as possible. We shall seek to perform a more comprehensive cytokine analysis using a multiplex platform in addition to the ten-analyte panel described above to increase the number of potential relationships that will be detected.

***Data Analysis Plan***

**Aim 1:**

The primary outcome will be LH pulse amplitude as assessed in the non-intervention frequent sampling study and compared to the early follicular phase study under treatment (i.e., either insulin + FFAs for Aim 1A or HFD for Aim 1B). LH pulsatility will be analyzed using a modification of the original Santen and Bardin method, as previously described and utilized by the PI in numerous studies. Up to 5 women will be assessed with frequent sampling prior to initiating the clamp portion of the study in order to confirm that diminished LH pulse amplitude is observed with the HFD. GnRH response will be compared between the non-intervention and intervention study as described above for gonadotropin pulsatility. We have used area under the curve methods to determine the LH response to exogenous GnRH and will utilize the same methodology as we have done in the past. FSH parameters will be compared between the non-intervention and intervention studies for both aims as described above for gonadotropin pulsatility. We will compare mean FSH, as pulsatility of FSH is less obvious than LH. We will compare changes in gonadotropin pulse frequency (for LH, and if we can detect distinct FSH pulses, we will compare FSH as well), mean LH and FSH and kinetics of LH, and if possible, FSH, before and after the intervention, as previously reported.

For Aim 1a, our preliminary data indicate that a sample size of 10 women should be sufficient to demonstrate short-term changes in gonadotropin amplitude, as LH pulse amplitude correlates well with mean levels in this setting. Moreover, we will be using a paired analysis. For Aim 1b, a sample size of 20 is estimated to have 80% power to detect a 25% decrement in LH pulse amplitude on the HFD using a 2 sided paired t-test, assuming  $\alpha=0.05$ , an untreated mean of 7IU/L, and a standard deviation of the difference of 1IU/ml. Urinary hormone profiles will be assessed for the entire cycle

**IRB #:** 15-1052  
**Project Title:** Reprometabolic Syndrome Mediates Subfertility in Obesity  
**Principal Investigator:** [name]

before and two cycles after initiation of the HFD using previously described menstrual cycle parameters suitable for urinary hormone determinations. The presumptive day of ovulation, called the Day of Luteal Transition (DLT) will be determined for all cycles that demonstrate a Pdg increment consistent with ovulation. Follicular and luteal phase lengths will be calculated, as will integrated follicular, luteal and whole cycle LH, FSH, E1c and Pdg. Whole-cycle parameters will be calculated and compared before and after HFD using a paired t-test for interval data, which can be reasonably fit by a linear model framework and in a linear regression model if adjustment for covariates is necessary. No statistical adjustment will be made for multiple comparisons of potentially covarying hormones. Hormones measured in daily urine will be modeled using linear mixed-effects regression to account for repeated measures nature of the data. Right-skewed variables will be analyzed on the log-scale, back-transformed and reported as geometric mean and 95% CI. We will also measure ovarian reserve markers: anti-Mullerian hormone (AMH; Ansh Laboratories), inhibin A and B (DSL, Webster, TX) before and after the intervention to determine whether they are altered by the intervention. All of these hormones have been previously measured by the PI. Activity will be monitored monthly during the entire study, and weekly during the month of HFD in all participants. The baseline cycle of collection will be used as the participant's benchmark and a deviation of >10% from baseline activity in any given week will alert the study staff to counsel the participant to maintain her usual level of activity.

Aim 2:

We do not have preliminary data on M or GRA in normal weight and obese reproductive aged women in our community with which to determine variation suitable for construction of sample size and power estimates. However, other, similar studies in normal weight, postmenopausal women in the Denver metro area have determined significant between group differences using a sample size of 12. We have therefore chosen a sample size of 15 to account for possible dropout, as paired analysis is essential for this aim. We also seek a slightly higher number in order to perform the association analyses described above.

Aim 3:

Exploratory Statistical Analysis: Testing the Mediation Hypothesis

Cytokines from the panel will be compared pre-and post-HFD using paired methodology. Cytokines that are significantly different after the HFD will be included in the mediation analysis. We will test that FFAs are correlated with change in the subset of selected cytokines. We will then test that change in the selected cytokines are correlated with drops in LH pulse amplitude. A linear regression model with change in LH pulse amplitude as the outcome will be estimated. Next a multivariable linear regression model with change in LH pulse amplitude as the outcome will be estimated, adjusted for change in cytokines. If multiple cytokines are identified for inclusion in this model, the correlation between change in cytokines will be assessed. If correlation between change in cytokines is greater than 0.3, a mixed model approach will be taken to control for cytokines and estimate the adjusted parameter for the

**IRB #:** 15-1052  
**Project Title:** Reprometabolic Syndrome Mediates Subfertility in Obesity  
**Principal Investigator:** [name]

effect of FFA on change in LH. Changes in inflammatory cytokines and adipokines will be associated with change in mean LH, LH pulse amplitude, estradiol (from the frequent sampling studies) and whole cycle integrated Pdg as above, using multiple linear regression modeling.

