***Study Design and Research Methods***

Consent/Screening Process:

A script for screening participants by telephone and by website survey who inquire in response to advertisements will be used, which will include the required verbal consent language. Participants who are eligible for enrollment will be asked to come to the Clinical and Translational Research Center (CTRC) for an intake examination and qualifying laboratory tests. Informed consent is obtained by the PI, the Professional Research Assistant, or an IRB approved designee, according to the scripted process, either when the patient comes in for the screening examination and tests or via a Zoom meeting or Telehealth with the PI or study coordinator. The informed consent discussion is always held in a private room that is free of distractions and participants are allowed the opportunity to ask questions and have their questions answered to their satisfaction before signing the informed consent document. If the participant completes the consent via Zoom meeting or Telehealth there will be a witness present and will sign the consent along with the participant. Once the Consent is signed we will request the

**IRB #:** 15-1052  
**Project Title:** Reprometabolic Syndrome Mediates Subfertility in Obesity  
**Principal Investigator:** [name]

participant to either scan the consent and email it to the Provider or take a picture with their cell phone and email it to the provider. The provider will print and sign the consent. With all signatures on the consent it will be scanned and sent to the participant. Once informed consent has been provided, baseline visit procedures are performed as outlined in the procedures section.

Study procedures:

For Aim 1a we will enroll 12 normal weight women to complete the study. For Aim 1b, we will enroll 20 normal weight women which may include women who participated in Aim 1A but not necessarily so.

Aim 1A will reproduce the reproductive phenotype of obesity in normal weight women by: infusing insulin and free FFAs in short term experiments and measuring gonadotropin pulsatility and pituitary GnRH response

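### Does the early look at LH pulse amplitude in up to 5 women on the high-fat diet bias the Aim 1b primary test?

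*Combined protocol and SAP*

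**What the plan says.** All references are to the combined protocol and SAP.

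- **Data Analysis Plan, Aim 1.** LH pulse amplitude, without intervention against on the diet, is the primary outcome. Up to 5 women have frequent sampling before the clamp portion starts, "in order to confirm that diminished LH pulse amplitude is observed with the HFD". The Aim 1b test is a two-sided paired t-test at 0.05 with 20 women.
- **Potential Scientific Problems, Aim 1.** The aim is a high-fidelity "model of hyperinsulinemia and elevated FFAs, which may require initial adjustment of our intervention"; the adjustments named are more simple carbohydrate "or a brief period of hypercaloric consumption) before proceeding with the full experiment".
- **Potential Scientific Problems, Aim 2.** "we will perform preliminary investigations to assure that the intervention is sufficient to cause detectable changes in gonadotropins", followed by "We will adjust our experimental design before we begin if it should be necessary".
- **Study Design and Research Methods, study procedures.** "For Aim 1b, we will enroll 20 normal weight women"; of Aims 2 and 3, "They will not require additional enrollment of study subjects or additional procedures". The only item called a pilot is the investigator's own two-week trial of the diet: "There were no subjects consented or enrolled".

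No section says what result counts as confirmation, what happens if LH does not fall, or whether the early women belong to the 20.

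**The concern.** The look is at the primary endpoint itself, on the intervention under test, and in a stated direction. Other sections allow the diet or the design to be adjusted. If the women stayed in the primary test because their LH fell, and would have been replaced had it not fallen, a quarter of the sample (5 of 20) would have been selected for the direction the study hopes to show. The unadjusted test would then favour a decrement.

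The enrolment counts suggest that the women are among the 20: Aim 1b enrols 20, Aims 2 and 3 add nobody, and the pilot enrolled nobody. The references to a later full experiment, and the recruitment ceiling of 60, leave a separate lead-in possible. The Aim 2 sample size of 15 equals 20 minus 5, but the plan attributes it to dropout, so it settles nothing. At stake are the main claim of Aim 1b and, less directly, the Aim 3 models that use change in LH amplitude as their outcome.

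**Working it through.** **Inputs from the Data Analysis Plan, Aim 1.** N = 20; two-sided paired t-test; alpha 0.05; decrement 25% of 7 = 1.75; SD of the difference 1 (its unit is printed as IU/ml and is read here as IU/L); early women up to 5, taken as 5.

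**The plan's own figure.** Power comes from the noncentral t with n - 1 degrees of freedom and noncentrality (1.75/SD) × √n. At SD 1 and n = 20 it exceeds 99.99%, not the stated 80%. N = 20 gives 80% only at a standardised effect of 0.660, that is, an SD of 1.75/0.660 = 2.65. This mismatch is a separate matter; here it means that bias should be looked at for both effect sizes.

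**Readings that the text supports**

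1. The 5 are the first of the 20, the look decides only when the clamps start, and all are kept on an unchanged diet. No selection occurs: lower-tail error 2.5%, bias zero.
2. The 5 are a separate lead-in and the test uses only women studied afterwards. Simulated lower-tail error is 2.5%, bias zero.

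**The reading that would cause bias (assumed).** Keep the 5 if they pass, add 15, and test 20; if they fail, enrol 20 new women once. The plan gives no criterion, so three are tried, with no true effect and 1,000,000 replicates each.

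| Assumed criterion | P(pass) | Lower tail, passing runs | Upper tail, passing runs | Bias, passing runs (SD) |
|---|---|---|---|---|
| Mean of 5 fell | 0.500 | 4.58% | 0.38% | -0.089 |
| 4 or more of 5 fell | 0.187 | 7.35% | 0.24% | -0.133 |
| One-sided p < 0.05 in the 5 | 0.050 | 12.53% | 0.06% | -0.195 |

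Two entries can be checked by hand. The bias for the first criterion is (5/20) × √(2/π)/√5 = 0.25 × 0.798/2.236 = 0.089. P(pass) for the second is (5 + 1)/32 = 0.1875.

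**Over all runs.** Lower tail = P(pass) × passing rate + (1 - P(pass)) × 2.5%:

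- Mean fell: 0.500 × 4.58 + 0.500 × 2.5 = 3.5% (simulated 3.55%)
- 4 of 5: 0.187 × 7.35 + 0.813 × 2.5 = 3.4%
- p < 0.05: 0.050 × 12.53 + 0.950 × 2.5 = 3.0%

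The same mixture with both tails gives two-sided errors of 5.0%, 5.5% and 5.4%. Overall bias is P(pass) × passing bias: -0.044, -0.025 and -0.010 SD.

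**If a failed check stops the study.** The lower tail is P(pass) × passing rate: 2.3%, 1.4% and 0.6%, all below 2.5%. Estimates in the studies that continue still carry the passing-run bias.

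**If the diet works.** At the plan's inputs (effect 1.75 SD), bias in passing runs is about 0.000, -0.003 and -0.012 SD, because the check is nearly always passed. At 0.66 SD it is -0.016, -0.055 and about -0.10 SD.

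**The case for a change.** The strongest case for acting is that the silence is real. The look is at the primary endpoint in the hoped-for direction, and the preliminary work described under Aim 2 is tied to gonadotropins with leave to change the design. The enrolment counts lean towards these women being in the test. Someone reading a significant result later could not tell from the plan whether 5 of the 20 had been retained for their direction. In runs where selective retention occurs, the lower-tail error is roughly two to five times nominal. If the diet changed after the look, pooling would also mix two interventions.

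What stands is that the rule is unwritten and that selective retention would favour a fall. What does not stand is the step to a biased plan. The sentence in the Data Analysis Plan links the look to the start of the clamps, not to membership of the analysis set. The diet adjustments are linked to insulin and fatty acids and placed before the full experiment. The design changes are placed before the start. The largest figure, 12.5%, arises only in the 5% of null studies that pass the strictest assumed criterion.

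Aim 3 adds no weight. The plan labels it exploratory, and no calculation shows that the look distorts the regression of LH change on cytokine change.

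**Conclusion.** The concern does not call for a change. The plan leaves one detail of the analysis set unstated, and the two ways of filling it that the wording supports are both unbiased: keep every early woman whatever her result, or keep all of them out as a lead-in. An analyst would choose one of these and report the choice. If the intervention had changed in between, the analyst would not pool the two groups.

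Even under the selective rule, which has to be assumed, the overall effect is modest. With no true effect and one restart, the lower-tail error is 3.0% to 3.6% against 2.5%, the two-sided error is 5.0% to 5.5%, and the overall bias is -0.01 to -0.04 SD. At the plan's stated effect and SD the bias in passing studies is about 0 to -0.01 SD. If the true effect were only 0.66 SD it would be -0.02 to -0.10 SD in passing studies.

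These figures rest on normal paired differences, exactly 5 early women, a single restart and the three assumed criteria. A rule that kept only the individual women whose LH fell would do more harm (null lower tail about 13%), but nothing in the documents suggests one.
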